11.1 Patient Replacement Policy

For subjects that fail to reach the primary endpoint and for whom the dataset is considered as not evaluable (i.e. patients who have failed to complete at least two weeks of study drug treatment), the next randomization assignment will be assigned to the next patient to be enrolled on the study in order to reach a minimum of 10 evaluable subjects in all cohorts and the targeted sample size of 30 evaluable subjects overall..

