6.2 Randomization

The randomization list will comprise three arms “CYT107 High frequency Arm” and “CYT107 Low frequency Arm”, and placebo Arm. A permuted-block randomization will be used in blocks of size of 3 and an allocation ratio of 1:1:1, stratified by study country (US and France). Subjects will be allocated randomly within each block. This procedure will be repeated until at

least 10 evaluable subjects are randomly assigned to each treatment group, totaling at least 30 evaluable subjects (between US and France).

Screening data, including lab results from screening and any relevant medical information, will be reviewed by the Research Nurse Coordinator and PI at each academic medical center for confirmation of all inclusion/exclusion criteria and randomization authorization.

After randomization authorization is granted by the PI at the responsible institution, the randomization assignment will be generated by computer. Each subject will be assigned the next available number. Subjects, investigators, and all study team members will be blinded to drug treatment. In the case of dropouts (either subject- or investigator-initiated), subjects will be replaced, to provide the required number of subjects. Randomization of replacements will be as follows:

1. Subjects withdrawn prior to randomization (prior to receiving CYT107 or placebo) will simply be replaced and the next subject will receive the same randomization assignment.
2. CYT107 treated subjects who are withdrawn after randomization while receiving the study drug treatments but prior to Day 14 will be replaced using with the next subject receiving the next randomization assignment. This will continue until a minimum of 10 patients have been randomized to each of the 3 cohorts and remained on study treatment through Day 13.
3. Subjects withdrawn or completing at least two weeks of study drug treatment will be considered evaluable and the following subject will receive the next scheduled randomization sequence.

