9.0 Statistical Analysis

9.1 Sample Size

Sample size justification

The primary endpoint of this trial is to compare two different dosing regimens of CYT107 to increase the absolute lymphocyte count (ALC), a marker of immunosuppression in sepsis which correlates with mortality. Although CYT107 has not been previously been used to treat patients with sepsis, there are data on the effect of CYT107 to increase the absolute numbers of CD4 and CD8 T cells in patients with cancer and in patients with HIV (see Figs 2&6 and reference #14). As demonstrated in Figs 2 & 6, CYT107 at a dose of 10 micrograms/kg (the dose that will be used in the present study) has a very predictable effect to cause a doubling of the number of CD4 T cells which are a major component of the absolute lymphocyte count (ALC) in patients with HIV. This effect to increase the absolute numbers of CD4 T cells was consistent in almost all patients who were treated with CYT107. CYT107 has a similar effect (although not quite as pronounced) on CD8 T cells. Therefore, we anticipate that greater than 80% of septic patients who are treated with CYT107 at a dose of 10 micrograms/kg (either high frequency dosing regimen or the low frequency CYT107 dosing regimen) will increase their ALC by over 50% by day 42, whereas less than 20% of patients who receive placebo will exhibit such a change. Under these assumptions, a simulation-based power calculation as implemented using the primary analytical plan listed in section 9.3.2. In particular, the proposed study design (10 subjects per treatment arm) was found to have greater than 85% power to detect an equal or more extreme treatment effect. Thus, we believe that 10 patients per group is sufficient to show a statistically significant effect of CYT107 to increase the ALC by over 50%.

Two other major goals of the study are to establish the safety of CYT107 in patients with sepsis and to determine that the pharmacokinetics and pharmacodynamics are not significantly altered in septic patients. CYT107 has been administered to over 300 patients and has been well tolerated with a low incidence of side effects. (see Investigator's brochure.)

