9.2.1.2 Analysis datasets

The following subsets of study participants will be defined and analyzed:

- 1) The **Safety dataset (SAF)** is defined as those subjects enrolled in the study, who have received at least one dose of study treatment.
- 2) The **Full Analysis Activity dataset (FAS)** is defined as all enrolled subjects who have received all the study treatment (5-low frequency, or 8-high frequency) administrations and have an evaluation of the primary Biological Activity Study End Point.
- 3) The **Per Protocol Activity dataset (PP)** is defined as all enrolled subjects who have been treated consistently with the protocol and have the evaluation of the primary Biological Activity Study End Point available. To be considered evaluable, patients in all study arms must complete at least 2 weeks of study drug treatment.

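### Recruiting to 10 two-week completers per arm does not secure 10 per arm in the Protocol's all-injections FAS, and the stated power above 85% has almost no reserve for the loss

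*Protocol*

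**What the plan says.** **Who counts towards the 10.** Protocol 11.1 treats as not evaluable "patients who have failed to complete at least two weeks of study drug treatment". Section 6.2 continues replacement "until a minimum of 10 patients have been randomized to each of the 3 cohorts and remained on study treatment through Day 13", with "an allocation ratio of 1:1:1". Section 4.2 sets the same two-week condition. Someone lost after that point is not replaced.

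**Who is analysed, Protocol.** Section 9.2.3 runs the primary logistic regression and overall likelihood ratio test separately in the PP and FAS sets. Under 9.2.1.2 the FAS is limited to enrolled subjects who "have received all the study treatment (5-low frequency, or 8-high frequency) administrations and have an evaluation of the primary" endpoint. No administration count is given for placebo. The PP set needs protocol-consistent treatment and an available endpoint, and it repeats the two-week condition.

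**When dosing ends.** Section 8.5 puts the last CYT107 dose on day 25 in the high-frequency arm and day 22 in the low-frequency arm. The Synopsis and 4.2 stop dosing at hospital discharge.

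**Power.** Section 9.1 assumes that "greater than 80% of septic patients who are treated with CYT107 at a dose of 10 micrograms/kg" will respond and that "less than 20% of patients who receive placebo will exhibit such a change". It reports that "the proposed study design (10 subjects per treatment arm) was found to have greater than 85% power".

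**Who is analysed, SAP.** The SAP analyses everyone who received at least one dose (the SAF) and tests the primary outcome with Fisher's exact test. It states no power.

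**The concern.** The number that stops recruitment and the number that enters the Protocol's FAS analysis are set by different rules. In the high-frequency arm four of the eight doses (days 15, 18, 22 and 25) fall after the two-week point. In the low-frequency arm two of the five CYT107 doses (days 15 and 22) do. In a population with high expected mortality, where recovery leads to discharge and discharge ends dosing, some two-week completers will not receive the rest.

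Two things follow. A reader of 9.1 will take 10 per arm as the analysed number and above 85% as the power of the primary test, and the recruitment rule does not secure either in the FAS. Also, a set called full analysis is in fact selected on surviving and on staying in hospital for more than three weeks, so comparing arms within it is not a comparison of the groups as randomized.

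**Working it through.** **Inputs**
- Responder rates 0.80, 0.80 and 0.20, and 10 per arm (Protocol 9.1).
- Overall likelihood ratio test across three arms, 2 df (9.2.3). Section 9.1 cites 9.3.2, a number the Protocol does not contain; 9.2.3 is the evident target.
- Alpha 0.05, stated only in the SAP and assumed here for the Protocol test.
- Mortality about 45% at 60 days (2.5), or 40-45% at 60-90 days (14.2).
- Loss between week 2 and the end of dosing or day 42: not given, so a range is used.

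**Step 1: reproduce the stated figure.** Enumerate every outcome (x1, x2, x3) for three binomial arms of size n. Reject when G = 2[Σ l(xi, n) − l(Σxi, 3n)] exceeds 5.99, where l(x, n) = x ln(x/n) + (n − x) ln(1 − x/n). Sum the probabilities of the rejected outcomes. At n = 10 the power is 86.0%, which agrees with the Protocol.

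**Step 2: vary the analysed number per arm**

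| n per arm | Power |
|---|---|
| 11 | 90.0% |
| 10 | 86.0% |
| 9 | 84.1% |
| 8 | 78.7% |
| 7 | 72.6% |

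Losing one patient per arm takes the power below 85%.

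**Step 3: random later loss.** Start from exactly 10 completers per arm, lose each independently with probability d, and average the power over the resulting arm sizes. Loss is taken as unrelated to response.

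| d | Average power | Chance all arms keep 10, (1 − d)^30 |
|---|---|---|
| 10% | about 83% | 4.2% |
| 20% | about 79% | 0.1% |
| 30% | about 73% | below 0.01% |

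**Step 4: FAS.** Assume a constant hazard and 45% mortality at 60 days. The share of day-14 survivors alive at day 25 is 0.55^(11/60) = 0.896, or about 9 of 10. Death alone therefore costs about 10% in the high-frequency arm. To day 22, the last counted CYT107 dose in the low-frequency arm, the share is 0.55^(8/60) = 0.923. Discharge before the last dose adds to this, but the documents give no figure for it.

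**Step 5: PP, only if the endpoint is the day-42 count.** Same constant-hazard assumption, from day 14 to day 42:
- 45% at 60 days: 0.55^(28/60) = 0.757, average power about 76%.
- 40% at 90 days: 0.60^(28/90) = 0.853, average power about 81%.

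**Step 6: the SAP's test.** Every two-week completer has been dosed, so the SAF has at least 10 per arm. At 10/10/10 the 3×2 Fisher test has 82.7% power. Fisher's test of pooled CYT107 (20) against placebo (10) has 87.5%. The SAP does not say which comparison is primary.

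**The case against.** The strongest reply is that the SAP has already settled the matter. It analyses all dosed patients, that set contains every two-week completer, and so 10 per arm is met. This stands for the SAP. A reader might infer that no planned analysis of the primary outcome reaches 10 per arm, and the documents do not support that. But 9.2.3 still names the FAS and PP, and the only stated power belongs to the Protocol's test. The SAF may exceed 10 per arm, but its additional patients stopped treatment early, so the 80% response rate need not hold for them.

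Second, a reader might infer that the PP set must also fall short. Section 9.2.3 counts a rise above 50% at any measurement up to day 42, and counts are taken from day 4. A two-week completer who dies on day 16 would normally have an evaluable endpoint, and the PP definition repeats the two-week rule. The PP shortfall arises only if the day-42 value is required, as in the Synopsis and 4.3.1.

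Third, 10 is a minimum. Arms can exceed it while the slowest one fills, and 11 per arm would give 90.0%. The right statement is that 10 per arm is not secured, not that it will be missed.

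Fourth, the size of the loss is not in the documents. The constant hazard is an assumption, and any share still in hospital at day 25 would be another. That limits how precisely the loss can be stated. It does not remove the point, because a 10% later loss already takes the average power below the claim.

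**Conclusion.** The point holds for the Protocol's FAS. Recruitment to two-week completers does not secure 10 per arm in a set that requires every administration. This is so under either reading of the endpoint, because the administration requirement alone excludes these patients. It holds for the PP set only under the day-42 reading, where the documents' own mortality figures and a constant hazard give about 76-81% power. It does not hold for the SAP's SAF, where the fault is different: the set and test differ from the Protocol's, and no power is stated for them.

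The claim of more than 85% is correct for exactly 10 per arm with the likelihood ratio test (86.0%), but it fails at 9 per arm. All these figures assume the 80/80/20 response rates, alpha 0.05 and loss unrelated to response. Wording should be corrected before analysis; the design itself need not change.

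**What to change.** 1. Make 9.2.3 and the SAP agree on one primary analysis set, one primary test (including which arms are compared) and one endpoint timing (any measurement up to day 42, or the day-42 value).
2. Stop using the all-injections FAS for primary inference. Keep it as a completers' sensitivity set under a name that says so, and state the administration count that applies to placebo.
3. In 9.1, say that 10 evaluable per arm means two-week completers, which may differ from the number analysed.
4. In 9.1, replace the single power figure with a range for the chosen set and test over stated losses. For the likelihood ratio test this would read: 86% with no loss from 10 per arm, about 83% with 10% and about 79% with 20%. If Fisher's test on the SAF is kept, give its power instead (82.7% for the 3×2 test at 10 per arm) and correct the reference to 9.3.2.

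The cost is wording in 9.1, 9.2 and the SAP, and a less favourable stated power. No extra patients are needed.

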11.2 Patients Lost to Follow-up

Participation is completely voluntary. At any time a patient and/or the PI may decide to discontinue study participation.

Every effort should be made to obtain information about patients who cannot be contacted for follow up. The research team should make reasonable attempts to collect at least minimum safety data on all randomized patients, to the extent of their abilities, in accordance with HIPAA regulations and IRB approval.

12. Adverse Events / Serious Adverse Events / Critical Events

12.1 Definitions

The following standard definitions for adverse events will be used:

Adverse event: An adverse event is any undesirable or untoward medical event (clinical or non-clinical e.g. abnormal laboratory/EKG/imaging results) which occurs in a patient or in a patient in a clinical trial, who is receiving a pharmacological product, and which is not necessarily causally related to the treatment.

Serious adverse event: A serious adverse event or reaction is any untoward medical occurrence that at any dose:

- results in death
- is life-threatening (the term “life-threatening” in the definition of “serious” refers to an event in which the patient was at risk of death at the time of the event; it does not refer to an event which hypothetically might have caused death if it were more severe.).
- requires inpatient hospitalization or prolongation of existing hospitalization
- results in persistent or significant disability/incapacity
- is a congenital abnormality
- is medically significant (event that may not result in death, be life-threatening, or require hospitalization may be considered serious when, based upon appropriate medical judgment, they may jeopardize the patient or subject and may require medical or surgical intervention to prevent one of the outcomes listed in this definition)

Unexpected Serious Adverse event: An unexpected adverse event is an event, the nature or severity of which is not consistent with CYT107 Investigator's Brochure (updated at least annually).

Critical event: The following events, occurring after the start of CYT107 and considered to be possibly or probably related to the study drug:

- Any grade ≥ 3 Adverse Event (clinical or biological)
- Rash \geq grade 2
- Any diagnosis of lymphoma confirmed by a pathologist
- Any adenopathy compromising or threatening organ function (e.g. mediastinal adenopathy inducing a respiratory distress; inguinal adenopathy inducing an edema of the lower limb; or any adenopathy threatening skin breakdown).
- Splenomegaly that is accompanied by:
 - 1) Clinical hypersplenism
 - 2) Suspicion of a diagnosis of splenic infarct (left upper quadrant pain and imaging study compatible with the diagnosis)
 - 3) Splenic rupture

12.2 Reporting of Adverse Events

12.2.1 Clinical and Biological Adverse Events

Any Adverse Events occurring for the time period between the signature of informed consent and the End of Study Visit, spontaneously reported by the patient or observed by others, will be recorded in the CRF and reported to the DSMB, RevImmune and IRB.

12.2.1.1 Nature and severity

The records will describe the nature, and the severity, using term and severity categories of the DAIDs "division of aids table for grading the severity of adult and pediatric adverse Events, Version 2.0.

According to previous clinical studies, Injection site reaction is frequently less than 5X5 cm. In consequence, with the objective of precisely determine the occurrence of any Injection Site Reaction the DAIDS (Division of Acquired Immunodeficiency Syndrome) has been adapted for this adverse event as follows:

Table 2 Division of AIDS Table (DAIDS 2.0) Toxicity Scale

PARAMETER	GRADE 1 MILD	GRADE 2 MODERATE	GRADE 3 SEVERE	GRADE 4 POTENTIALLY LIFE- THREATENING
Injection Site Pain or Tenderness Report only one	Pain or tenderness causing no or minimal limitation of use of limb	Pain or tenderness causing greater than minimal limitation of use of limb	Pain or tenderness causing inability to perform usual social & functional activities	Pain or tenderness causing inability to perform basic self-care function OR Hospitalization indicated
Injection Site Erythema or Redness¹³ Report only one > 15 years of age	2.5 to < 5 cm in diameter OR 6.25 to < 25 cm ² surface area AND Symptoms causing no or minimal interference with usual social & functional activities	≥ 5 to < 10 cm in diameter OR ≥ 25 to < 100 cm ² surface area OR Symptoms causing greater than minimal interference with usual social & functional activities	≥ 10 cm in diameter OR ≥ 100 cm ² surface area OR Ulceration OR Secondary infection OR Phlebitis OR Sterile abscess OR Drainage OR Symptoms causing inability to perform usual social & functional activities	Potentially life-threatening consequences (e.g., abscess, exfoliative dermatitis, necrosis involving dermis or deeper tissue)
≤ 15 years of age	≤ 2.5 cm in diameter	> 2.5 cm in diameter with < 50% surface area of the extremity segment involved (e.g., upper arm or thigh)	≥ 50% surface area of the extremity segment involved (e.g., upper arm or thigh) OR Ulceration OR Secondary infection OR Phlebitis OR Sterile abscess OR Drainage	Potentially life-threatening consequences (e.g., abscess, exfoliative dermatitis, necrosis involving dermis or deeper tissue)
Injection Site Induration or Swelling Report only one > 15 years of age	Same as for Injection Site Erythema or Redness , > 15 years of age	Same as for Injection Site Erythema or Redness , > 15 years of age	Same as for Injection Site Erythema or Redness , > 15 years of age	Same as for Injection Site Erythema or Redness , > 15 years of age
≤ 15 years of age	Same as for Injection Site Erythema or Redness , ≤ 15 years of age	Same as for Injection Site Erythema or Redness , ≤ 15 years of age	Same as for Injection Site Erythema or Redness , ≤ 15 years of age	Same as for Injection Site Erythema or Redness , ≤ 15 years of age
Injection Site Pruritus	Itching localized to the injection site that is relieved spontaneously or in < 48 hours of treatment	Itching beyond the injection site that is not generalized OR Itching localized to the injection site requiring ≥ 48 hours treatment	Generalized itching causing inability to perform usual social & functional activities	NA

¹³ Injection Site Erythema or Redness should be evaluated and graded using the greatest single diameter or measured surface area.

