The drug is well tolerated and the most frequent adverse events observed are local erythema at injection site. (12-14, 31)

Activity

[figure not shown]
Recent trials in HIV-infected patients have demonstrated a sustained dose-dependent increase in naïve and memory CD4⁺ and CD8⁺ T cells after administration of r-hCYT107 either with CYT 99 007 or CYT107.(12,30,31) In a prospective randomized placebo-controlled study, a single subcutaneous (SC) dose of r-hCYT107 was well tolerated with biologic activity demonstrable at 3 µg/kg and a maximum tolerated dose (i.e. without SAE or dose limiting toxicity) of 30 µg/kg. Single-dose of recombinant r-hCYT107 increased the numbers of circulating CD4⁺ and CD8⁺ T cells, predominantly of central memory phenotype. Levy et al.¹ published recently the preliminary results of the CYTHERIS study. These results were based on 13 patients who received a total of 8 subcutaneous injections of 2 different doses of r-hCYT107 (CYT 99 007); 3

or 10 µg/kg, 3 times per week (w) over a 16-day period. R-hCYT107 was well tolerated and induced a sustained increase of naive and central memory CD4+ and CD8+ T cells. (12)

We have now confirmed and extended our initial results with the completion of the INSPIRE study conducted in USA, Canada, France, Italy, utilizing the current glycosylated version of r-hCYT107 (CYT107) in HIV patients whose disease was well controlled by HAART but who remained immune non-responders with CD4+ T cells counts below 400/µL.

[figure not shown]
Results from INSPIRE patients confirmed the ability of CYT107 to produce a high quality immune recovery as shown in figure 2. The increases of CD4+ T cells counts induced by the three dosages of CYT107 administrations (10, 20 and 30 µg/kg/week) were significant when compared to the levels observed in the placebo arm (12).

Figure 2 Dose-dependent effect of CYT107 (CYT107) on CD4+T cells

At 20 µg/kg, CYT107 (CYT107) preferentially expanded Naive (N) and Central memory (CM) CD4+ as shown in figure 3.

[figure not shown]
Figure 3 Expansion of Naive (N) and Central Memory (CM) T cells after CYT107, 20 µg/kg

X axis is the ALC/µL. Y axis represents Days (D) or Weeks (W).

[figure not shown]
This expansion was associated with a significant decrease of the “PD-1⁺” exhausted CD4⁺ and CD8⁺ T cells as shown in figure 4:

Figure 4 Decrease of exhausted (PD1⁺) CD4⁺ and CD8⁺ T cells after CYT107

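### Table 2 was adapted to capture any injection-site reaction, but it gives no grade to an adult erythema or induration under 2.5 cm with no or minimal symptoms

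*Protocol*

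**What the plan says.** Protocol 12.2.1.1 introduces Table 2 with the experience of earlier studies: "Injection site reaction is frequently less than 5X5 cm". It then says that, "with the objective of precisely determine the occurrence of any Injection Site Reaction the DAIDS" scale has been modified for this event.

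For erythema or redness in patients over 15 years, Grade 1 is "2.5 to < 5 cm in diameter", or 6.25 to under 25 cm² in area, with no or minimal interference from symptoms. Grade 2 can also be reached at any size through "Symptoms causing greater than minimal interference with usual social & functional activities". For induration or swelling, each cell reads "Same as for Injection Site Erythema or Redness". The separate row for age 15 or younger starts Grade 1 at "≤ 2.5 cm in diameter". The footnote says that lesions "should be evaluated and graded using the greatest single diameter or measured surface area".

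Protocol 5.1 limits enrolment to ages 18 to 80. On past trials, Protocol 2.3.1.3 reports that "the most frequent adverse events observed are local erythema at injection site". The incidence and scoring of all adverse events belong to the primary safety endpoint (Synopsis; Protocol 4.3.1). Protocol 9.2.5.1 tabulates all treatment-emergent events, gives related events by grade, and counts a recurring event once per patient at its worst intensity. The SAP adds no rule on adverse-event grading, so the Protocol governs.

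**The concern.** The stated aim and the table do not match. The reason given for the adaptation is that reactions tend to be small, yet the adult rows set a floor at 2.5 cm and define nothing below it. An investigator who sees a 2 cm erythema in a patient without symptoms finds no adult category for it.

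This matters because scoring, and not only counting, is part of the primary safety endpoint, and local erythema was the most frequent event in earlier trials. Local tolerance is also less well known here: according to Protocol 3.2.1 the drug was until now given subcutaneously, whereas this trial prefers the intramuscular route. Without a rule, one site may call a small lesion Grade 1, another may leave the grade blank, and a third may treat it as below the threshold for a reaction.

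**Working it through.** **1. Check the table's own limits.** The area limits are the squares of the diameter limits:

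| Diameter (cm) | Square (cm²) | Area limit in Table 2 (cm²) |
|---|---|---|
| 2.5 | 2.5² = 6.25 | 6.25 |
| 5 | 5² = 25 | 25 |
| 10 | 10² = 100 | 100 |

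The limits reproduce exactly.

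**2. Can a lesion under 2.5 cm reach Grade 1 by area?** The footnote allows greatest diameter or measured area. For a given greatest diameter d, the largest possible area is that of a circle, π × d²/4. At d = 2.5 this is π × 6.25/4 = 4.91 cm², which is below 6.25. A circle needs a diameter of √(4 × 6.25/π) = 2.82 cm to reach 6.25 cm². The area alternative therefore never admits a lesion under 2.5 cm.

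**3. Can another adult category take it?**

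| Route | Open to an adult lesion under 2.5 cm with no or minimal symptoms and no local complication? |
|---|---|
| Grade 1 by diameter | No, the floor is 2.5 cm |
| Grade 1 by area | No, the area is below 4.91 cm² |
| Grade 2 by symptoms | No, it needs more than minimal interference |
| Grade 3 or 4 | No, it needs disabling symptoms or a complication such as ulceration or abscess |
| Row for age 15 or younger | No, enrolment starts at 18 |
| Pain and pruritus rows | No size floor, but they grade a different sign |

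The gap is confined to erythema/redness and induration/swelling, under 2.5 cm, with no or minimal symptoms and no complication.

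**4. Is such a reaction lost?** The adverse-event definition in Protocol 12.1 has no size limit. Protocol 12.2.1 requires any event that is reported or observed to be recorded. Protocol 7.1 directs special attention to injection sites at examination. The all-events table in Protocol 9.2.5.1 needs no grade. The reaction should therefore be recorded and counted, but it cannot be placed in a by-grade table.

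**5. Size.** By diameter, the ungraded band is 2.5/5 = half of the 0 to 5 cm range. That is a share of the scale, not of the reactions. The documents give no size distribution, so the share of reactions affected could lie anywhere from none to all. Because a recurring event counts once at its worst intensity, a patient is left without a grade for that event only if every occurrence falls in the gap. With at least 10 evaluable patients per arm (Protocol 6.2), one such patient moves a by-grade percentage by at most 1/10, or 10 percentage points.

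**The case against.** The strongest reply is that ungraded does not mean omitted. The recording rule and the all-events table do not depend on Table 2, and the DSMB reviews the severity grade that the investigator proposes (Protocol 10.2). This stands as far as incidence is concerned, and it limits the point to scoring and by-grade display. DSMB review may even out some differences between sites, but the DSMB would be working from the same table, which offers no adult category to confirm.

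It is also fair to say that the earlier experience may not carry over to a mainly intramuscular route. The Protocol does not forecast how common or how large local reactions will be here, which is one more reason to put no percentage on the effect.

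Three stronger readings are tempting, and the documents do not support them.

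- A reader might infer that small reactions disappear from the safety tables and that the comparison with placebo is pulled toward no difference. That would require the recording rule to be ignored. The same threshold also applies in all blinded arms, so no direction of bias can be shown.
- A reader might infer that the functional criteria push a sedated or ventilated patient to Grade 3 or 4 whatever the injection site looks like. Table 2 ties these criteria to symptoms, pain or tenderness as the cause, so incapacity from sepsis does not meet them. The self-care and hospitalization criteria stand only in Grade 4 of the pain row.
- A reader might infer an effect on critical events. A lesion with no grade, or one newly called Grade 1, does not reach the Grade 3 threshold in Protocol 12.1.

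**Conclusion.** The mismatch is real and narrow. Table 2 does not meet its own stated aim for adult erythema/redness and induration/swelling under 2.5 cm with no or minimal symptoms. The conclusion rests only on the table limits, the age range and the geometry above, and needs no assumption about reaction rates.

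The consequence is incomplete scoring of mild local reactions and room for sites to differ in a small trial. Overall incidence, critical events and the lymphocyte-count endpoint are unaffected if the Protocol's recording rule is followed. How many reactions fall in the gap cannot be determined from the documents. The unadapted scale is not reproduced either, so what the adaptation changed cannot be checked.

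**What to change.** Reconcile Table 2 with its stated aim. For patients over 15 years, define Grade 1 erythema/redness as any visible reaction under 5 cm in diameter (under 25 cm²) with no or minimal symptoms. Induration/swelling follows through its cross-reference. The two limits agree, since a lesion under 5 cm across covers less than π × 25/4 = 19.63 cm².

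Add a flag in the CRF for lesions under 2.5 cm, so that they can be tabulated separately and the Grade 1 count can also be shown with the present 2.5 cm floor. Removing the rows for age 15 or younger would be cosmetic and is not needed.

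The cost is a table edit, one CRF field and a completion note. No procedure is added, because injection sites are already inspected. The one small downside is that the reported rate of Grade 1 local reactions will rise.
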